1.3. OBJECTIVES

Primary Objective: To investigate the safety of Silverlon® dressing in patients throughout their prescribed course of radiation therapy and after radiation therapy.

- Hypothesis: We do not expect any adverse effects from extended use of Silverlon® dressing during and after radiation therapy.
- Primary Outcome Measures: Adverse reactions/events documented by the radiation oncologist as "probable" or "definite" related to Silverlon® Dressing (Weekly AE/Chart Review Source Doc).

Secondary Objective: To evaluate the feasibility of managing radiation dermatitis with Silverlon® dressing.

- Hypothesis: We expect that Silverlon® will be a feasible therapeutic modality for managing radiation dermatitis. We expect high compliance rate during RT and slightly lower when skin symptoms are not presented (i.e., before RT and post-RT). We do not expect any withdrawals due to adverse reactions to the dressing.
- Secondary Outcome Measures: Compliance; Withdrawal rate due to dressing.

Exploratory Objective: To monitor the severity of radiation dermatitis and patient quality of life during use of Silverlon® dressing throughout radiation therapy and after radiation therapy.

• Exploratory Outcome Measures: radiation dermatitis severity (RTOG Score & Radiation Induced Skin Reaction Assessment Scale (RISRAS)); DLQI

Page 7 of 41 RSRB STUDY00004587 Version Date: 09/14/2021 NCT04238728

[figure not shown]

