- The subject will also be given a **Silverlon® Compliance Log** to document each time they remove the Silverlon® dressing and put the Silverlon® dressing on. Study personnel will write the Subject ID, Subject Initials (First, Middle, Last (FML)) on the top of each page of the Compliance Log. Study personnel will write the date the Log was given to the subject in "Log Start Date" and write the date the Log was returned in "Log End Date". The "Log End Date" should correspond with the date that new Silverlon® dressings and new Log are dispensed to the subject (i.e., every 7 days).
- o It is anticipated that Baseline Visits will involve 30 minutes or less of the subject's time. This is a paper form that the subject will take home with them and complete as necessary daily whenever the Silverlon® dressing is removed and put back on.
- Additional Silverlon® Dressing will be provided to the subject every 7 days during the trial. A new Compliance Log will be given to the subject with two new Silverlon® Dressing every 7 days. For compliance reasons, subjects will return the used Silverlon® dressings and the completed Compliance Log to study personnel every 7 days when new dressings and log are dispensed.

Page 16 of 41 RSRB STUDY00004587 Version Date: 09/14/2021 NCT04238728

- Study personnel will complete additional information on the **OnStudy Data Form** using an EMR chart review to obtain demographic and medical history information: history of present illness, Tumor stage and TNM classification of breast cancer, body mass index (BMI), breast size, past medical history, body mass index, Fitzpatrick classification, previous chemotherapy or immunotherapy for breast cancer, prior surgery for breast cancer, and current medications.

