- Weekly during RT: During RT, the subject will have a scheduled clinic visit with their treating radiation oncologist. During this visit, the radiation oncologist will document the absence or presence of any adverse reactions/adverse events in their EMR chart note. Study personnel will review the EMR Chart note for documentation and description of the adverse reaction/event, intensity, relationship to Silverlon® dressing, action with Silverlon® dressing, treatment provided for reaction/event, and the outcome of reaction/event. Study personnel will electronically enter the data from the form into REDCap for secure storage in the study database. Study personnel may also be present at the weekly scheduled clinic visit to capture any AE-related information. The information will be entered into the Weekly AE/Chart Review Source Doc, which is an electronic REDCap form. Study personnel will enter any documented any adverse reactions, skin changes, and/or radiation treatment changes in the form.
- Study personnel will arrange to meet the subject every 7 days to provide to new Silverlon® dressings and Silverlon® Dressing Patient Instructions. This will occur until the subject completes the study. Study personnel will complete the Silverlon® Accountability Log to document the Subject ID, date, size, and number of Silverlon® dressings dispensed to each subject. This log will keep track of the amount of Silverlon® dressing on site in at University of Rochester. The investigator will contact Argentum if more Silverlon® dressings are needed.
- Weekly Phone Calls or Visits during RT: Study personnel will contact the subject by phone, email, or in clinic (as preferred by the subject) to ask the following 4 questions: 1) if they are wearing Silverlon® while sleeping; 2) having any discomfort while wearing Silverlon®; and 3) having any adverse reactions to the Silverlon®; if they feel Silverlon® is helping their skin. This information will be entered into an electronic REDCap form called the Questions Log. If the subject cannot be reached by phone, with prior permission a voicemail message will be left with the subject to return the phone call. The study personnel will follow-up with the subject within 24 hours by phone (or preferred mode of contact). All phone calls will be documented in the electronic Comprehensive Study Log. Study personnel may also meet with the subject in clinic during their scheduled radiation treatment appointment.

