 - The radiation oncologist will clinically assess the radiation-induced skin reaction in the breast area that Silverlon® dressing was applied. The radiation oncologist will rate the skin using the RTOG scale and the RISRAS-Healthcare Professional Assessment Scale. These ratings will be completed electronically in on a tablet (in REDCap).
 - O The subject will complete two survey forms that contain: **Dermatology Life Quality Index (DLQI) and RISRAS-Patient Symptom Scale.** The subjects will be asked to complete these forms by focusing on the whole breast to which the Silverlon® dressing has been applied. These surveys will be completed electronically on a tablet (in REDCap).
 - o **Digital photographs** of the skin in the radiation treatment area (where the Silverlon® Dressing has been applied) will be taken.
 - o Study personnel will also ask the subject: 1) if they are having any adverse reactions to wearing Silverlon®; 2) if they are wearing Silverlon® while sleeping; 3) having any discomfort while wearing Silverlon®; and 4) if they feel Silverlon® is helping their skin. This information will be entered electronically into the **Questions Log**.
 - Study personnel will also complete the Weekly AE/Chart Review Source Doc at this visit to document any adverse reactions, skin changes, and/or radiation treatment changes.
 - o Study personnel will remind the subject to continue wearing Silverlon® Dressing for two additional weeks (i.e., 14 days).
 - o This visit is estimated to involve 10 minutes of less of the patient's time.
- Study Personnel will perform an EMR chart review to obtain final radiation therapy information for the subject: positioning (prone vs. supine), total radiation dose, fractionation, boost dose (if any), bolus (if used), any delay in RT, any documented clinical complications, skin changes, or treatment changes. This information will be entered into the **EndRT Data Form**. This form can be completed electronically in REDCap or on paper and then entered into REDCap.
- Study personnel will contact the patient by phone (or preferred method of contact) at least 48 hours prior to their scheduled 2-week Post-RT Visit to remind them of the visit. All phone calls will be documented in the electronic **Comprehensive Study Log.**

Page 19 of 41 RSRB STUDY00004587 Version Date: 09/14/2021 NCT04238728

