- 2-Week Post-RT Visit: This visit will be scheduled with the subject at their scheduled last radiation treatment. Study personnel will meet with the subject with or after the radiation oncologist at this visit. Subjects will be reminded of this study visit at the phone call the previous week.
 - The radiation oncologist will clinically assess the radiation-induced skin reaction in the breast area that Silverlon® dressing was applied. The radiation oncologist will rate the skin using the RTOG scale and the RISRAS-Healthcare Professional Assessment Scale. These ratings will be completed electronically in on a tablet (in REDCap).
 - O The subject will complete two survey forms that contain: **Dermatology Life Quality Index (DLQI) and RISRAS-Patient Symptom Scale.** The subjects will be asked to complete these forms by focusing on the whole breast to which the Silverlon® dressing has been applied. These surveys will be completed electronically on a tablet (in REDCap).
 - o **Digital photographs** of the skin in the radiation treatment area (where the Silverlon® Dressing has been applied) will be taken.
 - O Study personnel will also ask the subject: 1) if they are having any adverse reactions to wearing Silverlon®; 2) if they are wearing Silverlon® while sleeping; 3) having any discomfort while wearing Silverlon®; and 4) if they feel Silverlon® is helping their skin. This information will be entered electronically into the **Questions Log**.
 - Study personnel will also complete the Weekly AE/Chart Review Source Doc at this visit to document any adverse reactions, skin changes, and/or radiation treatment changes.
 - o Study personnel will collect the final **Compliance Log** and used Silverlon® Dressings from the subject.

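### The dressing is worn for 14 days after radiation therapy, but the adverse-reaction question and chart review, weekly during therapy, recur only once, at the end of that period

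*Combined protocol and SAP*

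**What the plan says.** - **Objective and outcome (section 1.3).** The primary objective is "To investigate the safety of Silverlon® dressing in patients throughout their prescribed course of radiation therapy and after radiation therapy". The primary outcome counts "Adverse reactions/events documented by the radiation oncologist as" probably or definitely related to the dressing, taken from the Weekly AE/Chart Review Source Doc.
- **Wear after RT (section 5.1, EndRT Visit; also 5.2).** "Study personnel will remind the subject to continue wearing Silverlon® Dressing for two additional weeks (i.e., 14 days").
- **Active AE procedures (section 5.1).** The weekly oncologist visit with its chart review is headed as taking place during RT. So is the scripted contact: "Weekly Phone Calls or Visits during RT: Study personnel will contact the subject by phone, email, or in clinic (as preferred by the subject"). Section 11 places the weekly skin examination within the course of RT.
- **Dressing and log exchange (section 5.1).** Here the plan does go beyond RT: "subjects will return the used Silverlon® dressings and the completed Compliance Log to study personnel every 7 days". Of the 7-day meetings to supply dressings it says "This will occur until the subject completes the study". No adverse-reaction question is attached.
- **2-Week Post-RT Visit (section 5.1).** The oncologist examines the skin, staff complete the AE Source Doc, and the subject is asked "if they are having any adverse reactions to wearing Silverlon". The Questions Log item in section 5.3 is also in the present tense.
- **Schedule (section 15).** The AE Source Doc and Questions Log are marked at Weekly During RT, Mid-Study, EndRT and 2-Week Post-RT. Nothing falls between the last two.

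**The concern.** The objective names two phases, and the plan asks about reactions actively and often in only one of them. During RT a subject is asked every week. After RT she still wears the dressing but, on a literal reading, is next asked at day 14, and then only about what she is experiencing at that moment.

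This bears on the primary outcome for two reasons. First, only reactions that the oncologist grades as probable or definite count. Section 10.2 illustrates both grades with a compatible response to stopping exposure. A countable reaction may therefore be one for which the subject took the dressing off and improved, and such a reaction could be gone by day 14. Second, section 13.1 expects no events. A count of zero is most convincing when subjects were asked throughout the period it describes.

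**Working it through.** **1. The plan's own precision figures.** For 0 events in n subjects, the exact two-sided 95% upper limit is 1 − 0.025^(1/n).
- n = 30: 1 − 0.025^(1/30) = 0.1157 (section 13.1 states 0.116).
- n = 36: 1 − 0.025^(1/36) = 0.0974 (section 13.1 states 0.097).

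Both reproduce. They depend only on the count and on n, so a change in the contact schedule leaves them as they are.

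**2. Interval between scripted questions.** During RT it is 7 days. After EndRT the next scripted question is at the 2-Week visit, 14 days later. A question at day 7 would raise the scheduled questions in those 14 days from 1 to 2 and bring the interval back to 7 days.

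**3. Share of wear time.** Section 3.5 allows 15 to 20 fractions (short course) or 25 to 40 (conventional). Assume five fractions a week and a Monday start, which the documents do not state. With f fractions, RT spans 7(f/5 − 1) + 5 days, and wear continues for 14 more.

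| Fractions | RT days | Wear-days | 14 post-RT days as share |
|---|---|---|---|
| 15 | 19 | 33 | 42% |
| 20 | 26 | 40 | 35% |
| 25 | 33 | 47 | 30% |
| 40 | 54 | 68 | 21% |

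For 30 completers, days 1 to 13 after RT are 30 × 13 = 390 subject-days. This is calendar time between scripted questions. It is neither unobserved time nor a count of lost events.

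**4. What each other route would catch between EndRT and day 14.**
- *General AE monitoring (section 10.2)* runs from consent to study completion, and staff check reported reactions with the nurse or oncologist. It is described as recording what subjects volunteer.
- *Patient calls (section 11)* lead to a prompt oncologist appointment. The subject must start them.
- *The 7-day exchange (section 5.1)* is a contact with no scripted AE question.
- *The reminder call at least 48 hours before the 2-Week visit (section 5.1)* also has no scripted AE question.
- *The AE Source Doc at 2 weeks (sections 5.1 and 5.3)* is not limited to current events and records onset date and action taken with the dressing. The question that would prompt recall is in the present tense.
- *The DLQI at 2 weeks (section 5.3)* looks back one week, to about day 7 or 8, but does not ask about cause. The earlier days, 1 to 6 or 1 to 7, are 30 × 6 = 180 to 30 × 7 = 210 subject-days.
- *The 90-day contact (section 5.1)* asks about change since the 2-Week visit, so it does not reach back into this interval.
- *The Compliance Log (section 5.3)* has space for the reason for a removal. Sections 5.4 and 13.2 use it for wear time, and no step tells staff to review it for reactions.

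What remains is a reaction that begins and settles in days 1 to 13 and is never volunteered, even if a removal because of it is written in the log.

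**The case against.** The strongest reply is that the remaining case is narrow. A reaction bad enough to make the subject remove the dressing must then go unmentioned at the exchange, on the reminder call, by her own phone call, and in front of the oncologist at day 14. AEs elicited or volunteered must be documented whenever they surface (sections 9.2 and 10.1). An allergic reaction must be entered on the AE form (section 7). The link between countable reactions and removal of the dressing is itself an inference, because section 10.2 gives response to stopping as an example. No comparison of phases is planned, and nothing in the documents requires equal questioning before and after EndRT. Most of this stands, and it limits the weight of the point. It does not supply a scheduled look-back question.

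The weekly calls may also be meant to continue. The 2-Week visit text says "Subjects will be reminded of this study visit at the phone call the previous week", and section 5.4 has a weekly phone question on wear during sleep with no RT limit. The first sentence also appears for the Mid-Study and EndRT visits, and the second concerns sleep wear. Set against them are the explicit heading and the schedule column. If calls do continue, the interval stays at 7 days; the heading, the schedule and the question wording then need clarifying.

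Two stronger readings are tempting. A reader might infer that the two weeks after RT are unmonitored; the routes listed above show otherwise. A reader might also infer that the 2-Week visit records only current reactions. That is true of the scripted question but not of the AE Source Doc, which is to record any adverse reaction, with its onset date.

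**Conclusion.** The point holds as a cheap improvement of minor weight. Active questioning is less frequent in one of the two phases named in the primary objective. On a literal reading of section 5.1 and section 15, the interval between scripted questions doubles from 7 to 14 days, and the question that ends it does not look back.

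The effect on the event count cannot be estimated, because the documents give no rate for short-lived reactions after RT. A reader might infer that the upper limits of 0.116 and 0.097 are too low. Adjusting them would need an assumed share of reactions arising after RT and an assumed capture rate, and the documents supply neither. The limits stand as stated. The shares of wear time rest on the assumed five-fraction week and Monday start; the 14-day interval does not.

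**What to change.** 1. At about day 7 after RT, alongside the 7-day dressing exchange, ask the existing Questions Log items, with the adverse-reaction item worded *since your last radiation treatment*. Use phone or email if the subject is not seen in person, since section 5.1 promises no additional travel.
2. At the 2-Week visit, word that item *since our last contact*.
3. Check each returned Compliance Log for removals because of a reaction.
4. Enter any reaction found in these ways on the AE Source Doc and pass it to the radiation oncologist for attribution.
5. Add a day-7 post-RT column to section 15. If the weekly calls were always meant to continue, correct the section 5.1 heading as well.

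The cost is a few minutes per subject. At an assumed 5 minutes, that is 30 × 5 = 150 minutes (2.5 hours) to 36 × 5 = 180 minutes (3 hours) for the whole study. No new form, visit or staff is needed, and the sample size and planned precision do not change. More mild events may be recorded, but only those judged probable or definite enter the primary outcome.

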- 90-day Follow-Up: This follow-up by phone call, MyChart message or paper mail will occur 90 days from the start of RT and be scheduled with the subject at their 2-week Post-RT Visit. One or all three methods will be used to contact the subject as needed to complete the follow-up. Message text for copy/paste into MyChart has been included in Appendix A. For completion of the follow-up by paper mail, a pre-addressed and stamped envelope will be provided for the return of the paper response. For safety assessment, FDA recommends following patients up to 90 days. Study personnel will contact the subject to document an adverse reactions or skin reactions in the radiation treatment area to which Silverlon dressing was applied. Study personnel will ask the following questions: 1) Since your 2-Week Post-RT visit, has your skin reaction in the area where the Silverlon® dressing was applied improved, stayed the same, or worsened?; 2) Do you have any skin pain in the area where the Silverlon® dressing was applied? (yes/no); 3) Do you have any itching in the area where the Silverlon® dressing was applied? (yes/no); 4) Do you feel like your skin in the radiation treatment area has fully recovered? (yes/no); and 5) Would you recommend Silverlon® dressing to other patients during radiation therapy? (yes/no). For question 1, if the subject answers "worsened", study personnel will document the description of the skin reaction and notify the treating radiation oncologist to follow-up with the subject.

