7. SUBJECT WITHDRAWALS

Subjects will be advised during the consent process that they have the right to withdraw from the study at any time without prejudice or reason. Subjects that withdraw from the study will be replaced with another subject. Subjects will continue to receive radiation therapy as prescribed with standard of care with their treating radiation oncologist. The reason for discontinuation will be recorded in the subject's medical records. The date of occurrence and reasons for any subject withdrawal will be recorded and documented on the **Withdrawal Form**.

Subjects can be withdrawn from the study by the investigator or radiation oncologist for: non-compliance to study procedures; termination of funding; allergic reaction to Silverlon® dressing; worsening of the disease under study; intercurrent illness; pregnancy; or progression of skin reaction to RTOG score ≥3 in the radiation area where the Silverlon® dressing has been applied (i.e., whole breast). RTOG score ≥3 requires patients to have areas moist desquamation outside of skin fold regions (i.e., which would exclude inframammary fold and axillas because these are skin fold regions). Additionally, an area of moist desquamation that is >50% of the radiation treatment area (i.e., RISRAS-HPA score ≥3). Therefore, a large area of moist desquamation outside of skin folds would suggest withdrawal. Pinpoint areas and fold areas of moist desquamation could not require withdrawal. Patients withdrawn from the study will stop using Silverlon® dressing, but continue to receive radiation therapy on their normal schedule as prescribed by the treating radiation oncologist. For patients withdrawn from the study, standard of care for radiation dermatitis will be provided by the treating radiation oncologist, who will continue to follow the patient as per their normal clinical routine. The date of occurrence and reasons for any subject withdrawal will be recorded and documented on the Withdrawal Form. An adverse event will be reported if the skin reaction is RTOG ≥4. This grade of radiation dermatitis is severe and should be reported on the AE Source Doc and following reporting procedures stated in §10. Allergic reaction to Silverlon® dressing will be reported as an unexpected side effect on the AE Source Doc.

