13.2. Statistical Analyses

This is a safety study to determine Silverlon® dressing indication for radiation dermatitis. Descriptive statistics will be used to describe the study subject population. The primary analyses will evaluate the number of adverse events or reactions reported (if any) at the breast irradiation site where the Silverlon® dressing was applied. The primary analyses will be conducted on 30 fully evaluable subjects (i.e., 30 subjects that fully complete the study) and on all subjects that initiated treatment with Silverlon® dressing in an intent to treat analysis (see section 13.1). For a safety study, it is important to obtain the overall adverse event rate for all subjects that initiated treatment and all subjects who fully completed the study.

The secondary analyses will evaluate the compliance rates for the Silverlon® Dressing during RT and post RT. Compliance will be on the number of days during RT and post-RT that the dressing was worn. We expect compliance rate to be 97% (8). Additionally, we will evaluate the percentage of subjects that removed the dressing for sleeping. Subjects are asked to wear the dressing during sleep and only remove the dressing for RT sessions, showering/bathing, or swimming. Furthermore, we will calculate the number of hours during a day that the dressing was not worn summing the time between removal and application of the dressing each day.

Page 34 of 41 Version Date: 09/14/2021 Compliance will be evaluated in the 30 fully evaluable subjects. Although we can and will evaluate compliance in all subjects that initiated treatment, these analyses will not provide a complete picture of compliance due to early termination of study procedures. Furthermore, the secondary analyses will also evaluate withdrawal rates due to the Silverlon® dressing in all subjects who initiated treatment. We expect less than 6 subjects to withdraw due to the Silverlon® dressing. The exploratory analyses will assess trends in radiation dermatitis severity (i.e., RTOG and RISRAS) and quality of life (DLQI) during the course of the study. These analyses will also be able to evaluate changes in skin symptoms experience by the patient based on the RISRAS-Patient Symptom Scale during RT.

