Appendix A. 90-DAY FOLLOW UP FOR MYCHART

The following message will be sent to subjects through MyChart in order to complete the 90-Day Follow Up portion of the study.

Message Subject: Silverlon 90-Day Follow Up Questions

Message Body:

Dear [INSERT SUBJECT NAME],

Please answer the 90-Day Follow-Up questions below:

1. Since your 2-Week Post-RT visit, has your skin reaction in the area where the Silverlon® dressing was applied **improved**, **stayed the same**, or **worsened**?

If worsened, please describe:

Please answer the following questions with either "yes" or "no":

- 2. Do you have any skin pain in the area where the Silverlon® dressing was applied?
- **3.** Do you have any itching in the area where the Silverlon® dressing was applied?
- **4.** Do you feel like your skin in the radiation treatment area has fully recovered?
- **5.** Would you recommend Silverlon® dressing to other patients during radiation therapy?

Thank you,

[INSERT COORDINATOR NAME]

Page 41 of 41 RSRB STUDY00004587 Version Date: 09/14/2021 NCT04238728

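### Subjects withdrawn before the 2-Week Post-RT Visit have no stated route to the 90-day safety contact, so the day-90 data may mostly describe completers

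*Combined protocol and SAP*

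**What the plan says.** Section 5.1 gives the purpose of the late contact: "For safety assessment, FDA recommends following patients up to 90 days". Footnote 6 of the section 15 schedule likewise attributes the call to an FDA request. The contact "will occur 90 days from the start of RT and be scheduled with the subject at their 2-week Post-RT Visit", by phone, MyChart or paper mail.

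Question 1 begins "Since your 2-Week Post-RT visit, has your skin reaction in the area where the Silverlon® dressing was applied" (Appendix A, with the same wording in 5.1 and 5.3). An answer of worsened to this question is the only response for which the plan tells staff to notify the radiation oncologist. Questions 2 to 5 (pain, itching, full recovery, recommendation) do not mention the visit.

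Section 7 lists the grounds for withdrawal, among them "allergic reaction to Silverlon® dressing; worsening of the disease under study" and "progression of skin reaction to RTOG score ≥3 in the radiation area where the Silverlon® dressing has been applied". Section 11 also withdraws anyone who meets its adverse event definition. A withdrawn subject stops the dressing, is replaced, and is left to the treating radiation oncologist, "who will continue to follow the patient as per their normal clinical routine".

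Section 13.2 runs the primary analysis on the 30 fully evaluable subjects and also "on all subjects that initiated treatment with Silverlon® dressing in an intent to treat analysis". Section 3.1 says that withdrawn subjects count in the second set.

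**The concern.** The day-90 contact depends on a visit that an early-withdrawn subject does not have. Nothing else in the plan prompts it:

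- The Comprehensive Study Log (5.3) lists visits only up to the 2-Week visit, followed by completed, withdrawn or lost, and has no 90-day item.
- The Withdrawal Form records time and reason.
- Adverse event monitoring ends at study completion (10.2), which 5.2 equates with 14 days after RT.
- The schedule marks the weekly adverse event form only up to the 2-Week visit. After that, the 90-Day Phone Call Form is the only instrument.

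Withdrawal for a skin or allergic reaction is closely tied to safety, so day-90 data lost this way would be informatively missing. Because withdrawn subjects are replaced, a full set of 30 day-90 responses could be collected with the gap out of sight. Composite data go to FDA in support of the 510(k) application (section 14), and a completer-only day-90 summary could look more favourable than the experience of all treated subjects.

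**Working it through.** **Inputs.** 36 initiate and 30 complete (3.1, 13.1). Intervals are exact Clopper-Pearson, two-sided 95% (13.1). Eligible courses run from 15 to 40 fractions (3.5).

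**1. Reproduce the plan's limits.** With zero events in n subjects the upper limit is 1 − 0.025^(1/n).

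- n = 36: 1 − 0.025^(1/36) = 0.0974; the plan states 0.097.
- n = 30: 1 − 0.025^(1/30) = 0.1157; the plan states 0.116.

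The 13.1 row for 6 of 36 also reproduces, at 0.064 to 0.328.

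**2. Number who could lack day-90 data.** 36 − 30 = 6, and 6/36 = 16.7%. The plan calls this a 20% withdrawal rate; 20% of 36 would be 7.2. I use 6, the count in the plan's own tables.

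**3. What six missing contacts would do to a day-90 summary.** Suppose no late problem is reported by the 30 contacted and the other 6 are unknown.

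| Late problems among the 6 | Share of all 36 | 95% interval |
|---|---|---|
| 0 | 0 | 0 to 0.097 |
| 1 | 0.028 | 0.001 to 0.145 |
| 3 | 0.083 | 0.018 to 0.225 |
| 6 (assumed extreme) | 0.167 | 0.064 to 0.328 |

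A summary of completers alone would show 0 of 30, upper limit 0.116. In the same way, if all 30 report full recovery, the recovered share among the 36 lies between 30/36 = 83.3% and 36/36 = 100%, while completers alone show 100%. These are bounds; the documents give no basis for choosing a value inside them.

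**4. Time without a planned study contact.** Assume five fractions a week.

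- 15 fractions take 21 days, so the 2-Week visit falls at about day 35 and 90 − 35 = 55 days remain to the contact.
- 40 fractions take 56 days, so the visit falls at about day 70 and 90 − 70 = 20 days remain.
- A subject withdrawn at day 14 (assumed) would have 90 − 14 = 76 days with no study contact stated; at day 42 (assumed), 48 days.

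**The case against.** A reader might go further than the text allows in three ways.

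- **That withdrawn subjects never receive the contact.** The plan is silent; it does not exclude them. The date runs from RT start, footnote 6 sets no completion condition, and phone, MyChart or mail needs no prior visit. Staff could make the contact, but no instruction tells them to.
- **That the Withdrawal Form is the only record of the reaction.** Section 7 puts an allergic reaction, and RTOG 4 or above, on the AE Source Doc, and section 10 calls for all adverse events to be documented. The event behind such a withdrawal should already be captured. Its later course is what could be lost.
- **That the intent-to-treat adverse event rate is itself distorted.** Section 1.3 takes the primary outcome from the weekly form, and 13.2 specifies no analysis of the 90-day answers. As planned, a missing day-90 answer does not enter that rate directly.

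Three further limits are fair. Questions 2 to 5 can be answered by anyone who wore the dressing. A subject found to be RTOG 3 or above at the 2-Week visit has attended it and can be booked. Six of 36 is an all-cause allowance covering reasons such as non-compliance and intercurrent illness; section 1.3 expects no withdrawals from adverse reactions, and 13.2 expects fewer than six due to the dressing.

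On that last point the plan's figures do not all agree. Section 8 treats 6/15 (40%) as a two-fold increase, which implies a background near 20% for confluent moist desquamation, or 0.20 × 36 = 7.2 subjects. Skin-related withdrawal is therefore not remote on the plan's own numbers.

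After these concessions the gap remains: no stated route to the contact, and no usable question 1, for subjects withdrawn before the 2-Week visit.

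**Conclusion.** The point holds as a gap in the plan. Followed as written, the day-90 safety data would mostly describe completers, and those withdrawn early for a skin or allergic reaction would be the ones most easily left out. This affects resolution, later course and late events, and any day-90 summary given to FDA. It does not undermine the primary count.

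Up to 6 of 36 (17%) could lack day-90 data. This is an upper planning figure. It assumes that withdrawals match the plan's all-cause allowance, that all occur before the 2-Week visit, and that staff make no contact the plan does not ask for. The 83% to 100% range further assumes that all 30 completers report recovery and that a recovered proportion is reported, which 13.2 does not specify. The change is a cheap improvement and worth making.

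**What to change.** - **5.1, section 7 and section 15 footnote 6:** set the 90-day date from RT start at enrolment. Require the contact for every subject who initiated the dressing, including those withdrawn, unless she declines contact.
- **Question 1 (5.1, 5.3, Appendix A):** keep the present wording for subjects who attended the 2-Week visit. For those who did not, ask about change *since you stopped wearing the Silverlon dressing*. Apply the same notification after a worsened answer to both groups. Using the second wording for everyone would start the comparison in mid-irradiation for some subjects and after it for others, so the two versions should not be pooled as one measure.
- **13.2:** report the 90-day responses with all initiators as the denominator, state the number of missing contacts, and show completers and withdrawn subjects separately.

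The cost is about six extra calls or messages on the planning figures, plus edits to those sections, one form and Appendix A. No extra visit is needed.
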